##### 6.2.1.1 LAB ABNORMALITIES

**If cytopenias are deemed related to the underlying disease rather than ublituximab, dose reductions are not required, or are per investigator discretion.**

Worst CTCAE Grade Toxicity	Action to be Taken
Neutropenia	
Grade	Management
≤ Grade 1	No action required.
Grade 2	No action required; consider growth factor support.
Grade 3 or 4 1 st Occurrence	Hold until < Grade 3. Consider growth factor support per protocol requirement. Resume ublituximab at current dose cohort. Hold until < Grade 3. Consider growth factor support per protocol requirement. Resume ublituximab at current dose cohort.
Grade 3 or 4 subsequent Occurrences	Hold until < Grade 3. Consider growth factor support. Resume ublituximab at current dose cohort.
Management of neutropenia are per institution guidelines and if in the opinion of treating investigator, are appropriate for patient care.	

Worst CTCAE Grade Toxicity	Action to be Taken
Thrombocytopenia or Anemia	
Grade	Management
≤ Grade 1	No action required.
Grade 2	No action required.
Grade 3 or 4 1 st Occurrence	Hold until < Grade 3, or at subjects previous baseline. Resume ublituximab at current dose cohort.
Grade 3 or 4 subsequent Occurrences	Hold until < Grade 3, or at subjects previous baseline. Resume ublituximab at current dose cohort.
Management of thrombocytopenia and anemia are per institution guidelines and if in the opinion of treating investigator, are appropriate for patient care.	

Worst CTCAE Grade Toxicity	Action to be Taken
Elevated Liver Enzymes	
Grade	Management
≤ Grade 1	No action required.
Grade 2	No action required.
Grade 3 or 4 1 st Occurrence	Hold until < Grade 1, or at subjects previous baseline. Resume ublituximab at current dose cohort.
Grade 3 or 4 subsequent Occurrences	Hold until < Grade 3, or at subjects previous baseline. Resume ublituximab at current dose cohort.
Management of elevated liver enzymes are at the discretion of the investigator and should be discussed with TG Therapeutics.	

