### 3.3 DISCONTINUATION FROM TRIAL TREATMENT

---

Subjects will be discontinued from trial treatment for any of the following reasons:

- Disease progression, defined as 6 month confirmed disability progression ( $\geq 1$  point increase in the EDSS score)
- Irreversible or intolerable toxicity or abnormal laboratory values thought to be related to drug toxicity
- Patient requests to withdraw consent or discontinue treatment
- Pregnancy (see Section 3.3.1)
- Inability of the patient to comply with trial requirements
- Conditions requiring therapeutic intervention not permitted by the protocol
- Inter-current illness (this will be at the investigator's discretion)
- Non-compliance/lost to follow-up
- Discontinuation of the study by the Sponsor

If a patient withdraws from treatment during the first 4 weeks due to any reason other than DLT, that patient will be replaced.

After withdrawal from protocol treatment, subjects must be followed for AEs for 30 calendar days after their last dose of the trial drug. All new AEs occurring during this period must be reported and followed until resolution, unless, in the opinion of the investigator, these values are not likely to improve because of the underlying disease. In this case the investigators must record his or her reasoning for this decision in the subjects' medical records and as a comment on the electronic Case Report Form (eCRF).

All subjects who have CTCAE grade 3 or 4 laboratory abnormalities at the time of withdrawal must be followed until the laboratory values have returned to grade 1 or 2, unless it is, in the opinion of the investigator, not likely that these values are to improve because of the underlying disease. In this case, the investigator must record his or her reasoning for making this decision in the subjects' medical records and as a comment on the eCRF.

---

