## 6 DOSING DELAYS/DOSE MODIFICATION - RECOMMENDATIONS

Subjects should be assessed clinically for toxicity at each visit using the NCI CTCAE v4.0 (<http://evs.nci.nih.gov/ftp1/CTCAE/CTCAE>) grading scale.

Dosing will occur only if a patient's clinical assessment and laboratory test values are acceptable.

Dose modification and or intervention with supportive care recommendations for ublituximab is provided below, however final discretion lies with the treating investigator in regards to more or less aggressive intervention, if the investigational agent needs to be reduced, and actual dose reductions, as well as the number of dose reductions.

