### 6.1 CRITERIA FOR ONGOING TREATMENT

Repeat treatment should be administered per protocol provided that:

- Renal function should continually be assessed, with appropriate dose modifications as needed
- Recovered from grade 3-4 non-hematologic toxicity to grade 2 or less.
- Treatment may be delayed to recover from toxicity or per investigator discretion.
- No clinical or radiographic evidence of disease progression.

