#### 6.2.1 DOSE MODIFICATIONS OF UBLITUXIMAB

If toxicity, in the opinion of the investigator, is attributable to ublituximab, the following guidelines for neutropenia, thrombocytopenia, anemia, and elevated liver enzymes are recommended below (for Infusion Related Reactions, see Section 6.2.1.2). Final discretion lies with the treating investigator in regards to more or less aggressive dose reductions, as well as the number of dose reductions.

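### In the liver-enzyme table, the recommended threshold for resuming ublituximab is up to two grades looser after a recurrent Grade 3-4 elevation than after the first, with no reason given

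*Protocol*

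**What the plan says.** Protocol Section 6.2.1 offers its tables as recommendations that apply under one condition: "If toxicity, in the opinion of the investigator, is attributable to ublituximab". Section 6 adds that "final discretion lies with the treating investigator in regards to more or less aggressive intervention".

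The Elevated Liver Enzymes table in Section 6.2.1.1 then gives:

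- Grade 2 or lower: nothing needs to be done.
- Grade 3 or 4, first occurrence: "Hold until < Grade 1, or at subjects previous baseline. Resume ublituximab at current dose cohort".
- Grade 3 or 4, later occurrences: "Hold until < Grade 3, or at subjects previous baseline. Resume ublituximab at current dose cohort".
- Note under the table: "Management of elevated liver enzymes are at the discretion of the investigator and should be discussed with" the sponsor.

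Other protocol text bears on the same decision:

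- Section 6.1 sets a general condition for repeat treatment, "Recovered from grade 3-4 non-hematologic toxicity to grade 2 or less", without separating first from later events.
- Section 5.1.1 exempts from the dose-limiting toxicities a Grade 3 or higher ALT/AST rise that falls to Grade 2 or lower within 7 days.
- Section 5.2 is mandatory. If ALT or AST is above 5 times the upper limit of normal (ULN) before an infusion, the dose is held for up to 48 hours. Without recovery, the infusion is not given and the subject is withdrawn.

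The SAP contains no re-dosing rule.

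**The concern.** A re-dosing rule normally stays the same or tightens when a drug-attributed toxicity comes back. This one loosens. A subject with a second attributable Grade 3-4 liver event may, under the written default, be re-dosed at a higher enzyme grade than after the first, and at the same dose. Both rows are complete sentences, so this is not a gap left by redaction or text extraction. No rationale appears in either document.

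The stake is patient safety at the site. An investigator who looks up the table gets advice that contradicts itself, and two sites could reasonably act differently on the same case.

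**Working it through.** No planned figure needs reproducing here. The check compares the two rows and then asks how often the difference can matter.

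**1. Size of the gap.** On whole CTCAE grades, below Grade 1 means Grade 0, and below Grade 3 means Grade 2 at most. Each row also accepts a return to previous baseline, b. The highest grade at which dosing may resume is therefore max(0, b) after the first event and max(2, b) after a recurrence.

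| Baseline grade b | First event | Recurrence | Gap |
|---|---|---|---|
| 0 | 0 | 2 | 2 |
| 1 | 1 | 2 | 1 |
| 2 | 2 | 2 | 0 |

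Two grades is the maximum.

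**2. Comparison with the neighbouring text.**

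| Place | Highest grade accepted | Changes on recurrence? |
|---|---|---|
| Liver table, first event | 0, or baseline | – |
| Liver table, later events | 2, or baseline | Yes, looser |
| Neutropenia table | 2 | No |
| Thrombocytopenia/anemia table | 2, or baseline | No |
| Section 6.1, non-hematologic toxicity | 2 | No split |
| Section 5.1.1, ALT/AST exception | 2 (within 7 days) | No split |

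Only the liver table changes with recurrence. The comparators do not identify the wrong row. The later-event row agrees with every one of them, which suggests that the first-event row is too strict. However, the later-event row is also word for word the thrombocytopenia/anemia row, so it could have been carried over from that table.

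**3. Does Section 5.2 reconcile the rows?** No. It applies one cut-off to first and later events alike. The documents do not map grades to multiples of the ULN. If Grade 3 is assumed to start just above 5 times the ULN, a subject at Grade 2 passes the check, and the two rows still give different advice. If some Grade 2 values lay above 5 times the ULN, the check would narrow the practical gap. If some Grade 3 values lay below it, the check would block less.

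**4. Reach.** Infusions are on Day 1, Day 15 and Week 24, so only the last two can be affected. The later-event row needs two separate Grade 3-4 episodes first.

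- *Day 15.* There are 3 scheduled chemistry draws after first dosing (Day 2, Day 8, Day 15 pre-dose). Of the 2 × 2 × 2 = 8 high/not-high patterns, 1 shows two episodes: high, recovered, high. That subject is high at the infusion visit. Under the grade assumption in step 3, Section 5.2 governs, and the table matters only if enzymes fall to Grade 1-2 within 48 hours.
- *Week 24.* This is the main exposure. The interval from Day 15 is 168 − 15 = 153 days using the SAP target day (Section 2.5.3), or 180 − 15 = 165 days using Day 180 (Protocol Section 7.1.1; SAP Section 2.1.5). It has 6 scheduled draws: weeks 4, 8, 12, 16, 20 and 24 pre-dose.

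Section 8.1.1.3 lists ALT and AST increases as related events in at least 2 patients but under 10%. That figure is not limited to Grade 3-4 and says nothing about recurrence, so no expected count can be derived.

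**5. Weight of one affected subject.** Each cohort has 6 subjects assigned to ublituximab and 2 on placebo who cross over to the same regimen. The SAP Safety and ITT populations include everyone dosed with ublituximab. One subject is 1/(6 + 2) = 12.5% of a cohort with crossovers counted, or 1/6 = 16.7% without.

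**The case against.** The best defence is that the row that looks too loose is the protocol's ordinary standard. Section 6.1, the dose-limiting toxicity exception and every cytopenia row accept Grade 2, and the liver table itself asks for no action at Grade 2. On that reading, the first-event row is merely over-strict, and no subject gets less protection than the general rule gives. This stands as far as it goes: the first-event row is at least as likely to be the slip. It does not make the two rows consistent.

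The second defence is that other controls already deal with such cases. The table is advisory, and liver management is to be discussed with the sponsor. Dosing requires that a patient's "clinical assessment and laboratory test values are acceptable". Section 5.2 is mandatory, and Section 3.3 lists as a reason to stop treatment: "Irreversible or intolerable toxicity or abnormal laboratory values thought to be related to drug toxicity". These do limit the harm. None of them states which threshold applies after a recurrence, and a recommended default still guides practice.

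The third point is that copying the stricter threshold into both rows makes the table tighter than Section 6.1 and could cost a subject one of only three infusions. That is a fair cost. It is why the choice of threshold should remain open to the sponsor's confirmation.

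**Conclusion.** The inconsistency is real. The liver table loosens its recommended resume threshold on recurrence by up to two grades, without a reason, and at least one of its rows is wrong. It should be corrected, but its reach is small, and no endpoint, population, analysis or sample size changes.

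A reader might infer three stronger things that the documents do not support:

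- *That the recurrence row is the error and exposes subjects to unsafe re-dosing.* Grade 2 or less is what the protocol accepts elsewhere, so the first-event row may be the slip.
- *That the table lets a subject bypass the enzyme check before an infusion.* Section 5.2 is worded as mandatory and the table as a recommendation, so Section 5.2 prevails.
- *That a number of affected subjects can be predicted.* No rate of recurrent Grade 3-4 elevation is given.

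The size of the gap rests on whole-number grades and on the subject's previous baseline. The comparison with Section 5.2 also rests on the stated assumption about where Grade 3 begins.

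**What to change.** Use one threshold in both Grade 3-4 rows of the liver table, so that the recurrence threshold is no looser than the first-event threshold.

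- **Default:** below Grade 1, or previous baseline, in both rows. This is the conservative choice for a repeat liver event attributed to the drug.
- **Alternative:** if the sponsor confirms that the first-event row is the slip, below Grade 3, or previous baseline, in both rows. This agrees with Section 6.1. Because it relaxes the first-event row, a sentence of safety rationale should go with it.

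A line in Section 6.2.1.1 saying that Section 5.2 takes precedence is an optional clarification. Section 5.2 itself should stay as it is, and its 48-hour withdrawal rule should not be attached to the table's threshold.

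The editing cost is one table row. Under the default, the operating cost is a possible held or missed infusion, mainly at Week 24, with each affected subject weighing 12.5% of a cohort with crossovers counted (16.7% without). The alternative adds no held doses.

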### 6.2.1.2 INFUSION RELATED REACTIONS

Infusion related reactions have been reported with ublituximab. All subjects treated with ublituximab require pre-medication approximately 30 minutes prior to each dose of ublituximab or placebo with an antihistamine (diphenhydramine 50 mg or equivalent), and a corticosteroid (dexamethasone 10-20 mg or equivalent). Symptomatic infusion reactions, despite premedication, may be treated at the discretion of the treating physician, including but not limited to: oral acetaminophen 650 mg (or equivalent), corticosteroids, antihistamines, oxygen and bronchodilators.

#### 6.2.1.2.1 INFUSION RATE REDUCTIONS DUE TO INFUSION RELATED REACTIONS

The following are recommended infusion rate reduction/delay guidelines for subjects who experience severe Infusion Related Reactions (IRR's) in which treatment must be interrupted. Infusion rates should be considered targets for each respective cohort. If the treating investigator decides to interrupt the infusion or slow the infusion rate, then the reduction/delay and the reason for it must be noted on the eCRF and infusion log.

##### 1st Dose Interruption:

- The patient must be closely monitored until resolution of symptoms.
- Following the judgment of the Investigator, and provided vital signs are stable and normal saline has infused for at least 30 minutes, the infusion may be resumed at maximum 50% of previous rate.
- The rate should be increased by 50% every 30 minutes to the max rate of 100 mL/hr as long as tolerated.

##### 2nd Dose Interruption (same day):

- Wait approximately 2 hours. The patient should be closely monitored until resolution of symptoms.

If there is a second interruption of treatment due to IRR symptoms, ublituximab infusion must be stopped. The treating physician may decide whether to attempt completion of the infusion on a second day.

- If the dose discontinued is the Day 1 infusion, administration of the remainder of the dose on Day 2 is permitted as follows:
  - On Day 2, if patient symptoms have resolved, estimate remaining dose needed and prepare accordingly for infusion.
  - Begin infusion of remaining dose according to the infusion rate guidelines presented above for the first infusion of ublituximab.

If the patient has a dose interruption on Day 2, discontinue the infusion. The patient should again be monitored for all symptom resolution prior to release from trial site. The patient should start their next scheduled infusion at the protocol specific dose (Day 15) and infusion rate. If infusion rate reductions should be needed for the Day 15 infusion, please refer to the above recommendations. Final decision for infusion rate or discontinuation resides with the treating investigator.

## 7 STUDY EVALUATION TABLE

Baseline evaluations / laboratory tests are to be conducted within 28 days prior to Day 1. MRI scans used to identify measurable/evaluable disease are required to be done within 30 days prior to Day 1. In the event that the patient's condition is deteriorating, laboratory evaluations should be repeated within 48 hours prior to initiation of the next infusion.

Procedure	Screening	Baseline																Study End	
	D (-28 to 0)	W1 D1	W1 D2	W2	W3 D15	W4	W8	W12	W16	W20	W24	W24 (2 days post week 24 dose)	W25	W28	W36	W40	W44	W48	
Patient consent	X																		X 
Medical history	X																		
Serum Pregnancy test 	X																		
Urine Pregnancy Test 					X						X								
EDSS and Neurological Assessment 	X	X									X								X
Physical exam  & Vital signs (pulse rate, BP, temperature) 	X	X	X	X	X	X	X	X	X	X	X	X	X	X	X	X	X	X	X
Relapse Assessment		X	X	X	X	X	X	X	X	X	X	X	X	X	X	X	X	X	X
MRI 	X										X								X
12 Lead ECG 	X	X			X						X								
Blood collection for CBC and serum chemistry 	X	X	X	X	X	X	X	X	X	X	X	X	X	X	X	X	X	X	X
Blood collection for Immunologic analyses 	X	X	X	X	X	X	X	X	X	X	X	X	X	X	X	X	X	X	X
Fibrinogen 	X	X	X	X	X	X	X	X	X	X	X	X	X	X	X	X	X	X	X
PK analysis 		X		X	X	X					X		X						
Ublituximab Dose		X			X						X								
Serology: HIV, HCV, HBV, varicella 	X																		
Anti-drug Abs 		X			X	X		X			X				X				X
PT/INR		X																	
Quantitative Immunoglobulin 		X						X			X				X				X
Adverse events (CTC v4.0) 		X	X	X	X	X	X	X	X	X	X	X	X	X	X	X	X	X	X
Concomitant Medication 	X	X	X	X	X	X	X	X	X	X	X	X	X	X	X	X	X	X	X

-  For women of child bearing potential completed within 5 days prior to Day 1
-  To confirm negative HIV 1 and 2, HBV and HCV
-  Pre-dose on any day of infusion
-  Weeks 8 and beyond, collections/assessments may occur  $\pm 2$  days from specified time points
-  Prior to each dosing
-  Prior to and 15-30 minutes after each dosing on UTX treatment days; for non-treatment days, 1 PK sample should be obtained
-  To confirm potential development of human anti-chimeric antibodies
-  Physical exam will occur on all visits except Days 2 and 15 and weeks 2, 24 and 25
-  Pre-dose and post-dose on any day of infusion
-  Anti-drug antibodies are antibodies developed against ublituximab
-  EDSS Assessment will be assessed based on a slightly modified neurological examination as fatigue will not contribute to the EDSS assessment
-  Consent for open label extension study

## 7.1 OVERVIEW

---

All subjects should visit the study center on the days specified within this protocol. The complete schedule of assessments is shown in Section 7. The baseline physical examination with vital signs, medical history, evaluation of concomitant medications, EDSS (will be assessed based on a slightly modified neurological examination as fatigue will not contribute to the EDSS assessment), complete blood count/full blood count (3 part differential accepted), serum chemistry, and a baseline ECG should be done within 28 days prior to initiation of treatment. For women of child bearing potential, a serum pregnancy test should be completed within 5 days prior to Day 1. MRI scans should be performed  $\leq 30$  days prior to initiation of treatment. In the event that the patient's condition is deteriorating, laboratory evaluations should be repeated within 48 hours prior to initiation of the next infusion. Subjects who are in good health with stable disease and has completed the treatments and scheduled assessments through the final study visit may have the option of entering a 112 week open label extension study, with a continuation of treatment, and relapse and safety monitoring. Entry into the open label extension will require patient consent and fulfillment of entry criteria per the TG1101-RMS201E open label extension protocol.

### 7.1.1 LABORATORY EVALUATION

---

1. Hematologic profile: CBC/FBC with differential and platelet count should be obtained at:
  - a. For subjects initially treated with UTX:
    - i. Blood collection for CBC and serum chemistry at baseline, and day 1 (pre-dose), 2, 8, 15 (pre-dose), and week 4, 8, 12, 16, 20, 24 (pre-dose and 2 days post-dose), 25, 28, 36, 40, 44 and 48
  - b. For subjects initially treated with placebo followed by UTX treatment
    - i. Blood collection for CBC and serum chemistry at baseline, and day 1 (pre-dose), 2, 8, 15 (pre-dose), and week 4. Once the subject starts UTX treatment, blood collection for CBC and serum chemistry on day 1 (pre-dose), 2, 8, 15 (pre-dose), and week 4, 8, 12, 16, 20, 24 (pre-dose and 2 days post dose), 25, 28, 36, 40, 44 and 48
2. Serum chemistry should be obtained at the same schedule for hematologic profile (outlined above)

Serum Chemistry		
Albumin	Creatinine	SGOT [AST]
Alkaline phosphatase	Glucose	SGPT [ALT]
Bicarbonate	LDH	Sodium
BUN	Magnesium	Total bilirubin
Calcium	Phosphorus	Total Protein

Chloride	Potassium	Uric acid
----------	-----------	-----------

3. Serum pregnancy test should be obtained within 5 days prior to the initiation of therapy for women of childbearing potential.
4. PT/INR should be drawn on Day 1 prior to administration.
5. Quantitative immunoglobulin (IgG, IgM, IgA) test should be analyzed by a local laboratory on Day 1 (pre-dose), week 12, week 24 (pre-dose), and weeks 36 and 48.
6. Coagulant (Fibrinogen) tests will be obtained at the same schedule for hematologic profile (outlined above)

■ [REDACTED]

[figure not shown]
- a. Samples will be drawn from all subjects at Baseline (Day 1) prior to the first infusion of UTX and 15-30 minutes after the completion of the infusion; on Day 15 prior to the infusion of UTX and 15-30 minutes after the completion of the infusion; on Day 180 (week 24) prior to the infusion of UTX and 15-30 minutes after the completion of the infusion;

■ [REDACTED]  
[REDACTED]  
[REDACTED]  
[REDACTED]

■ [REDACTED]  
[REDACTED]  
[REDACTED]  
[REDACTED]

■ [REDACTED]

■ [REDACTED]  
[REDACTED]  
[REDACTED]  
[REDACTED]

### 7.1.2 RADIOLOGICAL EVALUATION

Assessment of effect on Gd enhancing lesion and new and enlarging T2 lesions will be evaluated as outlined in the schedule of events. For subjects initially treated with placebo, they will obtain a MRI at baseline and on week 4 (prior to start of UTX treatment).

Additionally, all study MRIs will undergo safety review by the site radiologist to identify any new clinical relevant abnormal MRI findings that are not consistent with the diagnosis of MS, with particular attention to the possibility of progressive multifocal leukoencephalopathy, and provide a report of the MRI to the treating physician.

### 7.1.3 NEUROLOGICAL EVALUATION

Assessment of effect on relapse rate will be evaluated as outlined in the schedule of events. For subjects initially treated with placebo, they will obtain a neurological evaluation at baseline and on week 4 (prior to start of UTX treatment). EDSS will be assessed based on a slightly modified neurological examination as fatigue will not contribute to the EDSS assessment.

